### **7.3 Data Analysis Plans**

The study will be performed as a reader confidence study. For each comparison, the average confidence scores and the corresponding standard deviations will be reported. Furthermore, to test whether the mean confidence score is larger than zero, a linear mixed effect will be used to analyze data, where the outcome variable is the confidence scores collected in this study and only a grand mean parameter is in the independent list. Additionally, a random intercept is used in the model to account for the correlation among readers when reading the images from the same patient. The Wald's test based on model fit will be used to test whether the grand mean parameter is larger zero. When the p-value from this test is less than 0.05, it will be concluded that there exists significant evidence that readers have more confidence with the s-DCT scatter corrected modality compared to the conventional s-DCT.

The reader preference study form (including both primary and secondary evaluations) is located in the Appendix.

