#### **4.3.3 Reader Study**

Three thoracic imaging specialty radiologists will be asked to separately evaluate the two sets of s-DCT images in a paired reader study. The radiologists will be presented with deidentified images from one modality (either with or without PSSC correction), then asked to identify the lesion and then determine a likelihood of malignancy based on the overall image set. A likelihood of malignancy score (1 to 10) will be initially assigned by the reader. The reader will then be given the deidentified images from the second modality, and their relative confidence in interpretation of the first modality as compared to the second will be evaluated on a 7 point scale. A washout period of four weeks will be provided and the images reviewed in reverse. Confidence scores in the evaluation of lung lesions, locations and involved structures will also be assessed. The CT scan is used as the gold standard to assess for the presence of a nodule and will be interpreted by consensus to identify the target nodule for each case.

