### **7.2 Sample Size and Accrual**

Assuming 50 cases are available for the comparison, and the standard deviation of the average reader score to be 2 (the range of the score is from +3 to -3), we will have at least 80% power to detect 0.7 confidence score of using scatter correction over without correction. In the data analysis, we will fit a linear mixed effect model with the confidence score as the outcome and a constant intercept. The working correlation matrix among readers is assumed to be compound symmetry. We will estimate grand mean from this model and test whether the mean confidence score is different from zero.

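### Does section 7.3 claim too much when it concludes that readers have more confidence, with no reader term in the model and no per-reader results promised?

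*Combined protocol and SAP*

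**What the plan says.** Section 4.3.3 fixes the readers: "Three thoracic imaging specialty radiologists will be asked to separately evaluate the two sets of s-DCT images in a paired reader study". Section 7.2 sizes the study on "Assuming 50 cases are available for the comparison" and takes "the standard deviation of the average reader score to be 2", on a scale from −3 to +3. It claims at least 80% power for a mean score of 0.7.

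In the model of section 7.3, "only a grand mean parameter is in the independent list". The random part is described as follows: "a random intercept is used in the model to account for the correlation among readers when reading the images from the same patient". A Wald test of the grand mean decides the matter. If p is below 0.05, the plan concludes that "readers have more confidence with the s-DCT scatter corrected modality compared to the conventional s-DCT". The descriptive commitment is this: "For each comparison, the average confidence scores and the corresponding standard deviations will be reported". Section 7.3 does not define a comparison. The reader form in the appendix has a field for the reader number.

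**The concern.** In a multi-reader study, cases and readers can both be sources of variation. This model allows for cases only. A conclusion about readers, with nothing to limit the word, can sound like a statement about radiologists in general. Such a statement would need between-reader variation in the standard error, and with three readers that could matter.

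The second worry is that a pooled mean conceals disagreement. Three mildly favourable readers and one enthusiast beside two indifferent colleagues can produce the same estimate, p-value and concluding sentence. The form's comparison items are organised by feature (shape/morphology, calcifications, architectural distortion), so the promised means and SDs are more naturally read as per item than per reader. If both worries held, a positive result could rest on one radiologist and be presented as a general finding.

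**Working it through.** **Inputs.** From the plan: 50 cases, SD of the per-case average score 2, and target mean 0.7 (section 7.2); three readers (section 4.3.3); p below 0.05 and a test that the mean exceeds zero (section 7.3). Assumed: complete data and one score per reader per case. The residual SD and the between-reader SD are not in the documents, so any value used below is an assumption.

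**1. The plan's power figure.** SE = 2/√50 = 0.2828, and 0.7/0.2828 = 2.475.
- One-sided 5%: Φ(2.475 − 1.645) = Φ(0.830) = 79.7%, which reproduces the stated 80% to rounding.
- Two-sided 5%: Φ(2.475 − 1.960) = Φ(0.515) = 69.7%, which does not.

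**2. What the standard error contains.** Write the score of reader j on case i as μ + rⱼ + bᵢ + eᵢⱼ. The case average over three readers is μ + r̄ + bᵢ + ēᵢ. The reader effects enter only through r̄, the same constant for every case, so they add nothing to the variance of the case averages. With balanced data and a positive estimated patient variance, the Wald SE is SD(case average)/√50 = 0.283. For the quantity μ + r̄, the average of these three readers, that is the correct standard error.

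**3. Does disagreement spoil the test?** The planned model was simulated with unbounded normal scores, an assumed within-patient correlation of 0.5 and 20,000 replicates. One-sided error was 5.5% when the readers did not differ and 5.2% when their means were +1, 0 and −1 (average zero). Disagreement does not inflate the error.

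**4. Does the pattern among readers affect the result?** The one-sided rule is met when the grand mean reaches 1.645 × 0.2828 = 0.465, that is, when the three reader means sum to 3 × 0.465 = 1.40. Means of (0.467, 0.467, 0.467) and (0, 0, 1.4) both give an estimate of 0.467, z = 0.467/0.2828 = 1.65 and one-sided p = 0.0495. At an average of 0.7, simulated one-sided power (5,000 replicates) was 79% for means of 0.7/0.7/0.7 and 81% for 1.5/1.2/−0.6. The test does not respond to the pattern, and any test of a balanced overall mean behaves in this way.

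**5. What a wider claim would cost.** For readers in general with between-reader SD τ, the SE would be √(0.080 + τ²/3), and the one-sided error of the planned test would be 1 − Φ(1.645 × 0.2828/SE).

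| Assumed τ | SE | One-sided error |
|---|---|---|
| 0 | 0.283 | 5.0% |
| 0.1 | 0.289 | 5.4% |
| 0.25 | 0.318 | 7.1% |
| 0.5 | 0.404 | 12.5% |

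**6. Does the plan make that wider claim?** Section 4.3.3 names three radiologists. Section 7.2 works with the average reader score and a grand mean. Section 7.3 models the scores gathered in this study, tests the grand mean, and draws its conclusion directly from that test in the same paragraph. Section 7.1 describes a single-center observational study, and section 1.5 presents the work as a pilot for a larger project. No section carries the result to other radiologists, so the error rates in step 5 apply to a claim that is not in the plan.

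**The case for a change.** The strongest case for the concern is that reader confidence is itself the primary endpoint. With only three readers, whether they agree is basic to interpreting the result, and a larger project is meant to follow. The data are already recorded by reader, and a small table would be informative. With an assumed residual SD of 1 to 1.5, a single reader's 95% interval has half-width 2.01 × √(4 + 2 × residual variance/3)/√50 = 0.61 to 0.67. Intervals for readers at 0 (at most −0.67 to 0.67) and at +1.4 (at least 0.73 to 2.07) would therefore not overlap.

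That stands as good reporting practice, and it is true that no section commits to per-reader means. It does not amount to a fault. The objectives and endpoint in sections 2.1 to 2.3 do not ask about agreement between readers. The commitment to report each comparison does not exclude a breakdown by reader. The interval widths rest on residual SDs that the documents do not give. They also rest on one score per reader per case, whereas section 4.3.3 describes a second reading in reverse order after a washout and the form has three comparison items. As for wording, the sentence seems open-ended only when it is separated from the test that triggers it.

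**Conclusion.** The concern does not hold. The planned analysis answers the question the plan poses: whether the three study readers, averaged, score the corrected images above zero. Its standard error of 0.283 and 5% error rate are right for that question, and treating the readers as fixed is a legitimate choice. A pooled mean cannot show agreement, but the plan does not say that it does. Limiting the sentence explicitly to the study readers and adding a per-reader table would leave the model, test, success rule, power and sample size as they are, so both are matters of reporting preference.

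This rests on complete, balanced data and on reading the conclusion within its own paragraph. If the result were later put forward for radiologists in general, the error rates in the table would become relevant, at a between-reader SD that the documents do not give.

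One separate matter is not settled here. Section 7.2 says the analysis will "test whether the mean confidence score is different from zero", while section 7.3 tests whether the mean exceeds zero, and the stated power fits only the one-sided test.

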### **7.4 Data Management**

The non-contrast chest CT, s-DCT, and SC s-DCT, if available, that are obtained of all eligible enrolled subjects will be de-identified for inclusion in the readers study. Copies of the clinical report forms as well as the de-identified images described in the preceding will be submitted for each case to the Study Coordinators for maintaining the study record and entering the data into a spreadsheet in preparation

for the reader study.

As an investigator initiated study, this trial will also be audited by the Lineberger Cancer Center audit committee every six or twelve months, depending on the participation of affiliate sites.

### **7.5 Teaching File**

After completion of the study, the de-identified study images will be developed into a teaching file by the PI. It will be used by the PI to educate radiologists in evaluating and interpreting s-DCT imaging.

## **8.0 STUDY MANAGEMENT**

### **8.1 Institutional Review Board (IRB) Approval and Consent**

It is expected that the IRB will have the proper representation and function in accordance with federally mandated regulations. The IRB should approve the consent form and protocol.

In obtaining and documenting informed consent, the investigator should comply with the applicable regulatory requirement(s), and should adhere to Good Clinical Practice (GCP) and to ethical principles that have their origin in the Declaration of Helsinki.

Before recruitment and enrollment onto this study, the patient will be given a full explanation of the study and will be given the opportunity to review the consent form. Each consent form must include all the relevant elements currently required by the FDA Regulations and local or state regulations. Once this essential information has been provided to the patient and the investigator is assured that the patient understands the implications of participating in the study, the patient will be asked to give consent to participate in the study by signing an IRB-approved consent form.

Prior to a patient's participation in the trial, the written informed consent form should be signed and personally dated by the patient and by the person who conducted the informed consent discussion.

### **8.2 Registration Procedures**

Study participants will be registered into OnCore®, a web based clinical research platform by one of the Study Coordinators.

### **8.3 Adherence to the Protocol**

Except for an emergency situation in which proper care for the protection, safety, and well-being of the study patient requires alternative treatment, the study shall be conducted exactly as described in the approved protocol.

### 8.3.1 Emergency Modifications

UNC investigators may implement a deviation from, or a change of, the protocol to eliminate an immediate hazard(s) to trial subjects without prior UNC's IRB/IEC approval/favorable opinion.

For any such emergency modification implemented, an IRB modification form must be completed by UNC Research Personnel within five (5) business days of making the change.

### 8.3.2 Single Subject Exceptions

Eligibility single subject exceptions are not permitted for Lineberger Comprehensive Cancer Center Investigator Initiated Trials under any circumstances. Other types of single subject exceptions may be allowed if proper regulatory review has been completed in accordance with Lineberger Comprehensive Cancer Center's Single Subject Exceptions Policy. Other Protocol Deviations/Violations

According to UNC's IRB, a protocol deviation is any unplanned variance from an IRB approved protocol that:

- Is generally noted or recognized after it occurs
- Has no substantive effect on the risks to research participants
- Has no substantive effect on the scientific integrity of the research plan or the value of the data collected
- Did not result from willful or knowing misconduct on the part of the investigator(s).

An unplanned protocol variance is considered a violation if the variance meets any of the following criteria:

- Has harmed or increased the risk of harm to one or more research participants.
- Has damaged the scientific integrity of the data collected for the study.
- Results from willful or knowing misconduct on the part of the investigator(s).
- Demonstrates serious or continuing noncompliance with federal regulations, State laws, or University policies.

If a deviation or violation occurs please follow the guidelines below:

**Protocol Deviations:** UNC personnel will record the deviation in OnCore®, and report to any sponsor or data and safety monitoring committee in accordance with their policies. Deviations should be summarized and reported to the IRB at the time of continuing review.

**Protocol Violations:** Violations should be reported by UNC personnel within one (1) week of the investigator becoming aware of the event using the same IRB online mechanism used to report Unanticipated Problems.

**Unanticipated Problems:**

Any events that meet the criteria for “Unanticipated Problems” as defined by UNC’s IRB must be reported by the study team using the IRB’s web-based reporting system.

**8.4 Amendments to the Protocol**

Should amendments to the protocol be required, the amendments will be originated and documented by the Principal Investigator at UNC. It should also be noted that when an amendment to the protocol substantially alters the study design or the potential risk to the patient, a revised consent form might be required.

The written amendment, and if required the amended consent form, must be sent to UNC’s IRB for approval prior to implementation.

**8.5 Record Retention**

Study documentation includes all eCRFs, data correction forms or queries, source documents, Sponsor-Investigator correspondence, monitoring logs/letters, and regulatory documents (e.g., protocol and amendments, IRB correspondence and approval, signed patient consent forms).

Source documents include all recordings of observations or notations of clinical activities and all reports and records necessary for the evaluation and reconstruction of the clinical research study.

Government agency regulations and directives require that all study documentation pertaining to the conduct of a clinical trial must be retained by the study investigator. In the case of a study with a drug seeking regulatory approval and marketing, these documents shall be retained for at least two years after the last approval of marketing application in an International Conference on Harmonization (ICH) region. In all other cases, study documents should be kept on file until three years after the completion and final study report of this investigational study.

**8.6 Obligations of Investigators**

The Principal Investigator is responsible for the conduct of the clinical trial at the site in accordance with Title 21 of the Code of Federal Regulations and/or the Declaration of Helsinki. The Principal Investigator is responsible for personally overseeing the treatment of all study participants. The Principal Investigator must assure that all study site personnel, including sub-investigators and other study staff members, adhere to the study protocol and all FDA/GCP/NCI regulations and guidelines regarding clinical trials both during and after study completion.

**10.0 APPENDICES**

**Scatter Corrected versus Uncorrected s-DCT  
 Reader Study**

Study # \_\_\_\_\_

Reader # \_\_\_\_\_

Date \_\_\_\_\_

**1. Confidence in the presence of a lesion:**

1	2	3	4	5
Definitely no lesion	Probably no lesion	unequivocal	Probably pulmonary lesion	Definitely pulmonary lesion

[figure not shown]
**If the confidence rating is 3 or greater (3, 4 or 5)**

**Lesion location (mark on figure):**

**Lesion size (measured in the coronal plane):**

**Presence of calcifications: Y / N**

**Comparing both modalities:**

**2. Scatter Corrected s-DCT versus Uncorrected: Shape/Morphology**

-3	-2	-1	0	+1	+2	+3
significantly less confident in the Chest Tomo representation	less confident in the CHEST TOMO representation	slightly less confident in the CHEST TOMO representation	have the same confidence in the CHEST TOMO	slightly more confident in the CHEST TOMO representation	more confident in the CHEST TOMO representation	significantly more confident in the CHEST TOMO representation

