### **2.2 Secondary Objectives**

The sensitivity of the scatter corrected s-DCT system to conventional s-DCT in the detection of lung nodules.

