## **3.0 PATIENT ELIGIBILITY**

### **3.1 Inclusion Criteria**

- 3.1.1 Patients with a known lung lesion(s)
- 3.1.2 Patients having undergone a chest CT
- 3.1.3 Patients 18 years of age and older
- 3.1.4 Patients able to provide informed consent

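### Level 3 of the reader form's lesion-presence scale is labelled *unequivocal*, which contradicts its mid-scale position, and location marking starts at that level

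*Combined protocol and SAP*

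**What the plan says.** Section 2.2 gives the secondary objective as "The sensitivity of the scatter corrected s-DCT system to conventional s-DCT in the detection of lung nodules". Section 7.3 names the instrument: "The reader preference study form (including both primary and secondary evaluations) is located in the Appendix". The reference is CT, which "will be interpreted by consensus to identify the target nodule for each case" (Section 4.3.3).

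The form opens with "1. Confidence in the presence of a lesion", scored 1 to 5. The anchors for 1, 2, 4 and 5 run in order from definitely no lesion to definitely a pulmonary lesion. The anchor for 3 is the one word *unequivocal*. The next instruction begins "If the confidence rating is 3 or greater (3, 4 or 5" and asks for the lesion's location, size and any calcification.

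Sections 4.3.3 and 7.1 to 7.3 do not say which rating counts as a detection, and Section 7.3 describes no analysis of sensitivity.

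**The concern.** To estimate sensitivity, each reading of a case must be classed as having found the target nodule or not. The form supplies two things for this: the 1 to 5 rating, and a location that can be compared with the CT target. The location is requested only from level 3 upwards, and level 3 is the one whose label and position disagree.

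By position, a 3 means undecided. By label, it means certain. If readers differ on this, or one reader wavers, the same number stands for different judgements. The form does not record which was meant, so nobody can sort the 3s afterwards. That is avoidable measurement error in the detection data.

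Every patient enters with a known lesion (Section 3.1). A lenient cut-off therefore raises sensitivity, and no lesion-free patients are planned who would show its false-positive cost.

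**Working it through.** **1. The plan's own figures.** The documents give no sensitivity estimate, target or sample size. The only calculation is the power statement in Section 7.2: 50 cases, SD 2, difference 0.7.

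- 0.7 / (2/√50) = 2.475
- One-sided 5%: Φ(2.475 − 1.645) = 79.7%, which matches the stated 80%
- Two-sided 5%: Φ(2.475 − 1.960) = 69.7%

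All inputs concern the −3 to +3 comparison score. Item 1 does not enter, so the primary analysis is untouched.

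**2. The scale set against its anchors.**

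| Level | Printed anchor (short) | Meaning implied by position | Location requested |
|---|---|---|---|
| 1 | definitely no | certain, absent | no |
| 2 | probably no | leaning absent | no |
| 3 | unequivocal | undecided | yes |
| 4 | probably yes | leaning present | yes |
| 5 | definitely yes | certain, present | yes |

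The five anchors line up with the five numbers, so this does not look like a table broken in extraction. Only level 3 is out of order.

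**3. What each reading of level 3 does.**

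- By position: the scale is properly ordered, and marking at 3 collects a location for undecided readings. Nothing is lost.
- By label: a reader sure of a lesion may choose 3 although 5 exists. A cut-off of 4 or greater then misses that detection, while a cut-off of 3 or greater still counts it if the mark matches the target.

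Section 4.3.3 plans three readers, so one reader supplies a third of the readings. If that reader gives 3 to a share q of cases when certain of the target, pooled sensitivity at 4 or greater falls by q/3. The documents give no value for q.

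**4. Dependence of sensitivity on the cut-off.** Let p3 be the share of readings rated 3 with a mark on the target. Then

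sensitivity(≥3) − sensitivity(≥4) = p3.

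Assume 60% of readings are rated 4 or 5, all marks match, and each reader rates each case once per image set (50 × 3 = 150 readings).

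| Assumed p3 | Readings rated 3 | Sensitivity ≥4 | Sensitivity ≥3 |
|---|---|---|---|
| 5% | 7.5 | 60% | 65% |
| 10% | 15 | 60% | 70% |
| 20% | 30 | 60% | 80% |
| 30% | 45 | 60% | 90% |

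**5. Dependence of the comparison on the cut-off.** difference(≥3) = difference(≥4) + p3(corrected) − p3(uncorrected). Assume 70% of corrected and 60% of uncorrected readings are rated 4 or 5.

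| p3 corrected | p3 uncorrected | Difference ≥4 | Difference ≥3 |
|---|---|---|---|
| 10% | 10% | +10 points | +10 points |
| 5% | 15% | +10 points | 0 |
| 5% | 20% | +10 points | −5 points |

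**6. A smoother illustration.** Assume normal latent ratings with SD 1, cut at −1.2, −0.5, 0.1 and 0.9, and a shift of 0.4 SD from correction. The gain at ≥3 is Φ(mean_c + 0.5) − Φ(mean_u + 0.5). The gain at ≥4 is Φ(mean_c − 0.1) − Φ(mean_u − 0.1).

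| Means, uncorrected / corrected | Share rated 3 | Gain ≥3 | Gain ≥4 | Ratio |
|---|---|---|---|---|
| 0.0 / 0.4 | 23% / 20% | 12.4 | 15.8 | 1.3 |
| 0.5 / 0.9 | 19% / 13% | 7.8 | 13.3 | 1.7 |
| 0.8 / 1.2 | 15% / 9% | 5.2 | 10.6 | 2.0 |

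Steps 4 to 6 give level 3 the same meaning for every reader. They show how far the cut-off matters under assumed values. They do not measure the effect of the wrong anchor.

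**The case against.** The strongest reply is that nobody will be misled. The readers are thoracic imaging specialists, a reader sure of a lesion has level 5 on the same line, and using 3 for certainty would rank it below probable. The word is almost surely a slip for *equivocal*. This stands as a judgement of likelihood, and it keeps the point small. It is no reason to leave a wrong word on the instrument before use.

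Three stronger inferences are tempting, and the reply to each is sound:

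- **That the form defines 3 or greater as a positive reading.** It does not. The instruction governs what is recorded, and no section links it to sensitivity.
- **That certain and uncertain readings are merged beyond repair.** The full 1 to 5 rating is kept, so 4 and 5 can be separated from 3 at any time. Only the intent behind a 3 is lost.
- **That the rule hides the confidence effect the trial looks for.** That effect is measured by the −3 to +3 items, which this threshold does not touch.

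It is also fair to say that 4 or greater is not the only defensible cut-off. A 3 with a mark on the CT target can reasonably count as a detection, because the location match tests it.

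**Conclusion.** The anchor at level 3 is wrong as printed and should be corrected before reading starts. The consequence is limited to the detection data for the secondary sensitivity objective. It depends on at least one reader following the label rather than the position, which is possible but probably uncommon.

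The size cannot be stated from the documents. The firm result is the identity in step 4: the two candidate sensitivities differ by the share of target-matched readings rated 3. From step 6 a reader might infer that the wrong word alters the apparent benefit of correction about two-fold. That is not supported: 2.0 is the top of a range from 1.3 under assumed values, and it reflects the choice of cut-off, not the anchor.

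The companion matter is that no detection cut-off is specified. A cut-off chosen after the ratings are seen would be open to challenge, because under some assumed shares the comparison disappears or changes sign.

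**What to change.** Before the first reading:

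1. On the form, replace *unequivocal* at level 3 with *equivocal (cannot decide)*.
2. Keep location, size and calcification marking at 3 or greater, so that no data are lost.
3. In Section 7.3, state which rating counts as a detection, and require the mark to match the CT target nodule. The choice of 3 or 4 is the sponsor's, provided it is made in advance.
4. Report sensitivity for both image sets at 3 or greater and at 4 or greater, with the chosen cut-off named as the main one.

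The cost is one label on the form, a short addition to Section 7.3, and one extra set of sensitivities in the report. Because the form is part of the protocol, the change goes through the amendment route in Section 8.4. Neither the sample size nor the primary analysis changes. Once reading is under way, the label can be corrected only for later readings.
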